### **10.5.2.5 ECOG performance status**

ECOG PS scale as described in [Section 7.2.2.4](#) will be used to assess physical health of patients. An analysis of time to definitive deterioration of the ECOG PS by one category of the score from baseline will be performed. Deterioration is considered definitive if no improvements in ECOG PS status is observed at a subsequent time of measurement during the treatment period following the time point where the deterioration is observed.

Patients receiving any further therapy prior to definitive worsening will be censored at their date of last assessment prior to start of therapy. Patients that have not worsened at the data cut-off point will be censored at the date of last assessment prior to start of therapy. Kaplan-Meier method will be used to estimate the distribution of time to definitive worsening and median time to definitive worsening will be presented along with a 95% confidence interval. A stratified log-rank test at one-sided 2.5% level of significance will be used to compare the distribution of time to definitive worsening between the 2 treatment arms.

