### **10.5.5 Patient-reported outcomes**

The EORTC QLQ-C30 questionnaire and the EuroQol EQ-5D-5L will be used to collect patient's QoL data. The BPI-SF will be used to assess patient's subjective assessment of cancer-related pain. The global health status/QoL scale score of the QLQ-C30 is identified as the primary patient-reported outcome variable of interest. Physical functioning, emotional functioning and social functioning scale scores of the QLQ-C30, the health status index score and overall health status of the EQ-5D-5L, and worst pain item (based on question 3), pain severity index, and pain interference indices of the BPI-SF are identified as secondary patient-reported QoL variables of interest.

Scoring of PRO data and methods for handling of missing items or missing assessments will be handled according to the scoring manual and user guide for each respective patient questionnaire (Fayers 2001; Oemar and Janssen 2013; Cleeland 2009). No imputation procedures will be applied for missing items or missing assessments. Five health states from the EQ-5D-5L will be converted to index values during the data analysis stage and will be further defined in the analysis plan. In addition, the visual analog scale (ranging from 0 to 100) will be evaluated for patient's rating of their overall health status.

The number of patients completing the each questionnaire and the number of missing or incomplete assessments will be summarized by treatment group for each scheduled assessment time points for each cohort. No formal statistical tests will be performed of PRO data and hence no multiplicity adjustment will be applied. The FAS will be used for analyzing PRO data.

Descriptive statistics will be used to summarize the scored scales of the QLQ-C30; health states, overall health status, and index values of the EQ-5D-5L, and the worst pain item (question 3), pain severity index, and pain interference indices of the BPI-SF at each scheduled assessment time point for each cohort. Additionally, change from baseline in the domain scores, health states, overall health status, and index values at the time of each assessment will be summarized.

[figure not shown]
[figure not shown]
Shift tables will be produced to describe worsening of pain from baseline based on the worst pain item from the BPI-SF. Patients with an evaluable baseline score and at least one evaluable post baseline score during the treatment period will be included in the change from baseline analyses.

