
[figure not shown]
[figure not shown]
In addition, a repeated measurement analysis model may be used to compare the two treatment groups with respect to changes in the domain scores (global health status/QoL scale score, physical functioning, emotional functioning and social functioning scale scores of the QLQ-C30 index score and overall health status of the EQ-5D-5L, longitudinally over time. [REDACTED]

[figure not shown]
Time to definitive 10% deterioration in the global health status/QoL, physical functioning, emotional functioning, social functioning will be assessed. The time to definitive 10% deterioration is defined as the time from the date of randomization to the date of event, which is defined as at least 10% relative to baseline worsening of the corresponding scale score or death due to any cause. If a patient has not had an event, time to deterioration will be censored at the date of the last adequate QoL evaluation. The distribution will be presented descriptively using Kaplan-Meier curves. Summary statistics from Kaplan-Meier distributions will be determined, including the median time to definitive 10% deterioration along with two-sided 95% confidence interval. Additionally, time to definitive deterioration with different cutoff definitions (e.g. 5%, 15%) may be specified in the RAP as deemed appropriate. A stratified Cox regression will be used to estimate the hazard ratio (HR), along with two-sided 95% confidence interval.

[REDACTED]

[REDACTED]

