The global health status/global QoL scale score of the EORTC QLQ-C30 is identified as a primary PRO variable of interest. The physical functioning, emotional functioning and social functioning sub-scale scores of the EORTC QLQ-C30, the visual analog scale (VAS) of the EQ-5D-5L, and worst pain item (based on question 3), pain severity index, and pain interference indices of the BPI-SF are identified as secondary PRO variables of interest. High scores in the EORTC QLQ-C30 represent a higher response level. Thus a high score for a functional scale represents a high / healthy level of functioning; a high score for the global health status / QoL represents a high QoL, but a high score for a symptom scale / item represents a high level of symptomatology /problems. Higher scores in the EQ-5D-5L also correspond to better health states. A higher score in BPI-SF corresponds to more pain.

The number of patients completing PRO questionnaires and the number of patients missing/expected to have PRO assessments will be summarized by treatment arm for scheduled assessment time points (the number of ongoing patients will be used as

denominator). Furthermore, the amount and the pattern of missing data may be explored by treatment arm and over time using summary statistics. The following categories will be used to describe whether the questionnaire was completed at a specific time point:

- yes, fully completed
- yes, partly completed
- no.

Scoring of raw data and methods for handling missing items or missing assessments will be handled according to scoring manuals for each respective patient questionnaire (Fayers 2001; Oemar and Janssen 2013; Cleeland 2009).

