Analysis of the time to definitive 10% deterioration in the primary and the secondary PRO variables of interest will be performed. Definitive 10% deterioration is defined as a worsening in score by at least 10% compared to baseline, with no later improvement above this threshold observed during the treatment period, or death due to any cause. Time to deterioration is the number of days between the date of randomization and the date of the assessment at which deterioration is seen. If a patient has not had an event prior to analysis cut-off, start of new anti-neoplastic therapy, lost to follow-up, end of treatment or withdrawal of consent, the time to deterioration will be censored at the date of the last evaluation before the earliest of these times. Only assessments collected while the patient is on treatment and on or before the end of treatment visit will be included in the PRO time to deterioration analysis. If deterioration is observed after two or more missing assessments, time to deterioration will be censored at the date of the last assessment prior to the deterioration. The rules for calculating number of missing assessments are the same as those for tumor assessments (see details in Section 2.5.5). Time to 10% deterioration in the global health status/QOL scale, and secondary PRO scales of interest as listed above, will be compared between the two treatment arms using a

stratified log-rank test (strata based on IRT data) at 2 sided 5% level of significance. The survival distributions will be presented descriptively using Kaplan-Meier curves. Summary statistics from the Kaplan-Meier distributions will be determined, including the median time to 10% deterioration and the proportions of patients without 10% deterioration at 2 month intervals. Both point estimates and 95% CIs will be presented. A stratified Cox regression model will be used to estimate the hazard ratio (HR) of time to deterioration, along with 95% confidence interval. Sensitivity analysis of time to definitive deterioration with different cut-off definitions (e.g. 5%, 15%) may also be considered if the number of events per arm is judged sufficient to draw relevant conclusions.

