4.2 Time-to-event analyses

The following sections present a general methodology to be used to analyze the following time-to-event variables:

- Progression-free survival
- Overall survival

- Time to definitive deterioration of the ECOG score by one category of the score from baseline
- Time to response: defined as the time between date of randomization until first documented response (CR or PR) according to RECIST
- Time to definitive deterioration of PRO scores (e.g., global health status/QoL, physical functioning, emotional functioning, social functioning scales of the EORTC QLQ-C30, and the VAS of the EQ-5D-5L)
- Time to onset of safety events
- Duration of safety events
- Time to first chemotherapy or death
- Time to first chemotherapy
- Duration of response
- [REDACTED]

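### The primary-analysis SAP tests time to 10% deterioration on 8 to 10 PRO scales at two-sided 5%, although protocol 10.5.5 rules out formal PRO tests

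*SAP*

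**What the plan says.** **Protocol 10.5.5 (Patient-reported outcomes).** The rule on testing is explicit: "No formal statistical tests will be performed of PRO data and hence no multiplicity adjustment will be applied". On time to deterioration the section says "Time to definitive 10% deterioration in the global health status/QoL, physical functioning, emotional functioning, social functioning will be assessed", and then "The distribution will be presented descriptively using Kaplan-Meier curves". A stratified Cox hazard ratio with a two-sided 95% confidence interval is added. No log-rank test appears in the visible text, part of which is redacted.

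**Primary-analysis SAP 3.8.2.7.** Global health status/QoL is the primary PRO variable. Three further QLQ-C30 scales, the EQ-5D-5L VAS, BPI-SF worst pain, the pain severity index and the "pain interference indices of the BPI-SF are identified as secondary PRO variables of interest". Time to 10% deterioration on the primary scale and on the listed secondary scales is then compared between arms by a "stratified log-rank test (strata based on IRT data) at 2 sided 5% level of significance". Only the survival curves are called descriptive.

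**SAP 4.2 (Time-to-event analyses).** The list of time-to-event variables includes "Time to definitive deterioration of PRO scores (e.g., global health status/QoL, physical functioning, emotional functioning, social functioning scales of the EORTC QLQ-C30" and the EQ-5D-5L VAS. These five are given as examples and no BPI-SF scale is among them.

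The final-CSR SAP lists the PRO objective but specifies no PRO analysis, so the point concerns the primary-analysis SAP only.

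**The concern.** The protocol's only reason for not adjusting PRO results for multiplicity is that they are not formally tested. The SAP introduces tests with a stated significance level and still does not adjust, so the protocol's reason no longer applies. It also widens the analysis from four scales to between eight and ten.

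Time to 10% deterioration in global health status is a listed secondary endpoint (Protocol Table 3-1). A p-value below 5% from 3.8.2.7 could therefore be reported as a significant finding from a pre-specified test, when the protocol says that no such test exists. What is at stake is which quality-of-life claims the trial may make.

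**Working it through.** **1. Can the two texts be reconciled?**
- *Version.* The SAP rests on protocol amendment 2, and the protocol at hand is amendment 4. The visible change lists for amendments 2, 3 and 4 record no change to 10.5.5.
- *Declared departure.* The SAP change history for 3.8.2.7 covers the mixed model, a linear model at selected times and additions to the time-window table. It mentions neither a log-rank test nor a departure from 10.5.5. A later entry changes the EQ-5D-5L variable in order to match the protocol, so agreement with it was intended.
- *Exploratory label.* A sentence restricting the use of exploratory tests sits in SAP 3.9.7, under other safety data. Nothing in 3.8.2.7 labels the PRO tests nominal or exploratory.
- *Protocol practice elsewhere.* Where the protocol wants a test it says so, for example for ECOG status: "A stratified log-rank test at one-sided 2.5% level of significance will be used to compare the distribution of time to definitive worsening". For PRO deterioration it does not.

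No visible text reconciles them.

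**2. How many tests?** From SAP 3.8.2.7:
- QLQ-C30: global health, physical, emotional and social = 4
- EQ-5D-5L VAS = 1
- BPI-SF worst pain and severity index = 2
- BPI-SF interference indices = 1 to 3 (Protocol 7.2.6.3 defines activity, affect and overall)

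Total: 4 + 1 + 2 + (1 to 3) = 8 to 10. The visible protocol text names 4.

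**3. What does that imply with no true effect?** The documents give no PRO power, event count or correlation, so there is no planned figure to reproduce. Assume k standard normal test statistics with common correlation r. With u the shared normal factor,

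P(at least one two-sided p<0.05) = 1 − ∫ [Φ((1.96 − √r·u)/√(1−r)) − Φ((−1.96 − √r·u)/√(1−r))]^k φ(u) du

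| k | r = 0.9 | r = 0.7 | r = 0.5 |
|---|---|---|---|
| 4 (scales in the visible protocol text) | 9.4% | 13.0% | 15.6% |
| 5 (examples in SAP 4.2) | 10.2% | 14.8% | 18.3% |
| 8 | 11.9% | 19.1% | 25.0% |
| 10 | 12.8% | 21.3% | 28.7% |

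The chance of at least one false result favouring ribociclib is 6.0%, 9.5% and 12.5% for k = 8, and 6.4%, 10.7% and 14.4% for k = 10.

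Whatever the correlation, the expected number of p-values below 5% is 8 × 0.05 = 0.4 to 10 × 0.05 = 0.5.

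**4. Does dropping the test lower this rate?** No. A Cox 95% interval that excludes 1 is nearly the same event as a log-rank p<0.05. In 4,000 simulated null trials per correlation setting, the two disagreed on whether any scale was positive in at most 0.2% of trials. The simulation assumed 484:243 patients, eight scales, an 18-month median and 7 to 26 months of follow-up, and was unstratified.

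**The case against.** The best reply is that this is a labelling matter with little practical risk. PRO lies outside the PFS-then-OS hierarchy. Protocol 10.5.5 itself allows a repeated-measures model to compare the arms, so between-arm PRO comparisons are not foreign to it. The SAP makes that longitudinal model, reported with 95% intervals, the main PRO analysis. Readers are told in the protocol that PRO results are unadjusted. Part of 10.5.5 is redacted, and no report is visible in which a PRO p-value was claimed as significant.

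Most of this stands, and it limits the point to reporting. It does not remove the conflict. Permission to compare arms in a model is not permission for 8 to 10 log-rank tests at a 5% level, and the sentence excluding formal PRO tests is fully readable.

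A reader might also object that the error rates in the working do not measure any harm that the fix cures. That is right. They show only why an unlabelled p<0.05 here should not be read as confirmatory.

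**Conclusion.** The conflict is real and should be corrected. The SAP formally tests PRO time to deterioration where the protocol says that it will not, on more scales than the visible protocol text names, with no adjustment and no nominal label. Across 8 to 10 scales the chance of at least one p<0.05 with no true effect is about 12-13%, 19-21% or 25-29% at correlations of 0.9, 0.7 or 0.5. The correlations and the common-correlation structure are assumptions. Death counts as an event on every scale, which pushes the correlation up and these rates down.

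Four stronger readings are not supported:
- *That PFS or OS type I error is inflated.* Both are controlled separately from PRO.
- *That all secondary-endpoint tests breach the protocol.* ORR, CBR and ECOG deterioration are tested because the protocol plans it.
- *That the false-positive chance is 34% to 40%.* Those figures (1 − 0.95^8 = 33.7%; 1 − 0.95^10 = 40.1%) need independent scales, and these scales come from the same patients and share deaths.
- *That the deterioration rule fails for BPI-SF patients who start at 0.* The SAP says "Definitive 10% deterioration is defined as a worsening in score by at least 10% compared to baseline". Ten percent of 0 is 0, so the wording can be read to count any sustained rise. The programming specifications, which might settle it, are not available.

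**What to change.** 1. Replace the log-rank sentence in SAP 3.8.2.7 with: *Time to definitive 10% deterioration will be summarised by Kaplan-Meier curves and stratified Cox HRs with 95% CI; these are descriptive, not adjusted for multiplicity, and no claim of significance will be made.*
2. Label any PRO time-to-deterioration p-values already produced as nominal.
3. Identify the EQ-5D-5L VAS and BPI-SF deterioration analyses as additions to the four scales named in the visible protocol text.

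At most, also report the convention that was used for BPI-SF scores of 0 at baseline.

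The cost is wording. PRO collection stopped with protocol amendment 4 and the final-CSR SAP plans no PRO analysis, so the change falls on how the primary-analysis PRO results are described. No re-analysis is needed.

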3.9 Safety evaluation

The assessment of safety will be based mainly on the frequency of adverse events and on the number of laboratory/ECG values that fall outside of pre-determined ranges. Other safety data (e.g. vital signs and special tests) will be considered as appropriate.

All safety outputs will use the safety set. The safety summary tables will include 'on-treatment' events/assessments, i.e. those collected on or after the first date of study treatment and collected no later than 30 days after the date of last study treatment administration. The AEs started before the first dose but worsening during the treatment period are also considered as 'on-treatment' events. All safety events/assessments will be listed and those collected outside of the on-treatment window will be flagged.

3.9.1 Adverse events (AEs)

3.9.1.1 Coding of AEs

Adverse events are coded using the Medical Dictionary for Regulatory Activities (MedDRA) terminology.

3.9.1.2 Grading of AEs

AEs will be assessed according to the Common Terminology Criteria for Adverse Events (CTCAE) version 4.03.

The CTCAE represents a comprehensive grading system for reporting the acute and late effects of cancer treatments. CTCAE v4.03 grading is by definition a 5-point scale generally corresponding to mild, moderate, severe, life threatening, and death.

If CTCAE grading does not exist for an adverse event, grades 1 – 4 corresponding to the severity of mild, moderate, severe, and life-threatening will be used. CTCAE grade 5 (death)

will not be used in this project; if an AE results in death it will be documented in the outcome (“fatal”). Information on deaths will also be collected on the ‘Death’ CRF.

3.9.1.3 General rules for AE Reporting

AE summaries will include all AEs starting on or after study Day 1 (i.e. on or after the day of the first intake of study treatment) and starting no later than 30 days after the last administration of study treatment (see [Section 2.1.5](#)). All AEs will be listed. AEs starting prior to study Day 1 and AEs starting later than 30 days after the last treatment date will be flagged in the listings.

AEs will be summarized by presenting the number and percentage of patients having at least one AE, having at least one AE in each primary system organ class, and for each preferred term using MedDRA coding. A subject with multiple occurrences of an AE will be counted only once in the AE category.

Separate AE summaries will be presented by primary system organ class, preferred term, and maximum grade. A patient with multiple grades for an AE will be summarized under the maximum grade recorded for the event. AE with missing CTCAE grade will be included in the ‘All grades’ column of the summary tables.

In AE summaries the primary system organ class will be presented alphabetically and the preferred terms will be sorted within primary SOC in descending frequency. The sort order for the preferred term will be based on their frequency in the ribociclib arm.

The frequency of grade 3 and 4 AEs will be summarized separately.

Any information collected (e.g. grades, relationship to study treatment, action taken etc.) will be summarized and listed as appropriate.

3.9.1.4 AE summaries

The following adverse event summaries will be produced by treatment group:

- Summary of deaths and adverse events
- Adverse events, irrespective of causality, by primary system organ class, preferred term and maximum grade
- Adverse events with suspected relationship to study treatment by primary system organ class, preferred term and maximum grade
- Most common grade 3-4 adverse events, irrespective of causality, by preferred term and maximum grade (greater than x% in either arm)
- Adverse events, irrespective of causality, by primary system organ class and maximum grade
- Adverse events, irrespective of causality, by preferred term and maximum grade
- Adverse events with suspected relationship to study treatment by preferred term and maximum grade

- Grade 3 or 4 adverse events, irrespective of causality, by primary system organ class, preferred term and maximum grade
- Grade 3 or 4 adverse events with suspected relationship to study treatment by primary system organ class ,preferred term and maximum grade
- On treatment deaths by preferred term
- Deaths, by primary system organ class and preferred term
- Serious adverse events, irrespective of causality, by primary system organ class and preferred term and maximum grade
- Serious adverse events with suspected relationship to study treatment, by primary system organ class, preferred term and maximum grade
- Adverse events leading to study drug discontinuation, irrespective of causality, by primary system organ class, preferred term and maximum grade
- Adverse events leading to study drug reductions, irrespective of causality, by primary system organ class, preferred term and maximum grade
- Adverse events leading to study drug interruptions, irrespective of causality, by primary system organ class, preferred term and maximum grade
- Adverse events requiring additional therapy, irrespective of causality, by primary system organ class, preferred term and maximum grade
- Non-serious adverse events (at least x% incidence rate in either treatment arms) by primary system organ class and preferred term
- Serious and non-serious adverse events with number of occurrences (an occurrence is defined as >1 day between start and prior end date of record of same preferred term)
- On-treatment deaths and SAEs with fatal outcome, by SOC and PT

AEs of interest will also be summarized. See [Section 3.9.1.5](#) for the grouping details.

3.9.1.5 Grouping of adverse events of special interest

An adverse event of special interest is a grouping of adverse events that are of scientific and medical concern specific to ribociclib. These groupings are defined using MedDRA terms, SMQs (standardized MedDRA queries), HLGs (high level group terms), HLTs (high level terms) and PTs (preferred terms). Customized SMQs (Novartis MedDRA queries, NMQ) may also be used. A NMQ is a customized group of search terms which defines a medical concept for which there is no official SMQ available or the available SMQ does not completely fit the need. It may include a combination of single terms and/or an existing SMQ, narrow or broad. For each specified AESI, the number and percentage of patients with at least one event of the AESI occurring during the on-treatment period will be summarized.

Summaries of these AESIs will be provided by treatment arm, (specifying grade, SAE, relationship, leading to treatment discontinuation, leading to dose adjustment/interruption, etc.).

A Case Retrieval Sheet (CRS) with the exact composition of the AE groupings is to be used to map reported AEs to the AESI groupings. This file may be updated (i.e. it is a living document) based on review of accumulating trial data, and therefore the groupings are also subject to potential change. Table 3-6 provides the latest groupings at the time of the finalization of the SAP, from the CRS dated 13Dec2016. The most up-to-date version of the CRS will be used at the time of the analysis.

Table 3-6 AESI groupings

AESI grouping	MedDRA category
Anemia	SMQ
Diarrhea	SMQ
Hepatobiliary toxicity	SMQ
Infections	SMQ and SOC
Leukopenia	HLT
Nausea, emesis	HLT
Neutropenia	HLT and PT
Pneumonitis, interstitial lung disease	SMQ
Pulmonary embolism	SMQ and HLT
QTc prolongation	SMQ
Renal impairment	SMQ
Reproductive toxicity	SMQ
Thrombocytopenia	SMQ

